### **Cardiovascular Events**

- The following cardiovascular events will be collected. Major Adverse Cardiovascular Events (MACE) defined as:

- Non-Fatal Myocardial Infarction: The presence of at least 2 of the 3 following criteria: 1) chest pain consistent with angina, 2) abnormal values of cardiac enzymes (> ULN of the MB fraction of creatinine phosphokinase and/or troponin that follows a pattern of myocardial injury), 3) myocardial injury current (ST segment elevation) or the development of new Q waves in 2 contiguous leads of the electrocardiogram.
- Non-Fatal Stroke: ischemic or hemorrhagic stroke defined as an acute, focal neurologic event that persisted for > 24 hours. If neurologic symptoms last for < 24 hours but magnetic resonance imaging (MRI) confirms an infarct, it will be considered as a stroke. Confirmation by imaging studies (magnetic resonance imaging or computerized tomography of the brain) will be sought in all cases, but will not be an absolute requirement for consideration of the event.
- Cardiovascular deaths: including any death from a cardiovascular cause including: myocardial infarction, stroke, heart failure, arrhythmic death, aortic dissection or rupture, any fatal thromboembolic event, sudden cardiac death, any death of unknown cause and unwitnessed death.
- Congestive heart failure defined as: hospitalization or prolonged (> 12 hours) emergency department visit due to dyspnea, shortness of breath, with progressive edema accompanied by clinical findings of pulmonary vascular congestion. Radiographic and/or echocardiographic documentation is desirable but not required. Treatment by intravenous (Parenteral) diuretics or inotropes is required to confirm this diagnosis versus ultrafiltration, hemodialysis or left ventricular assist devices.

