### 3.6.3.4 AEs of Special Interest

Incidence of IRs, anaphylaxis, gout flares and Major Adverse Cardiovascular Events (MACE) will be summarized for the safety analysis set by infusion duration group. Separate summaries will be produced for adjudicated events and reported events (only applies to IRs, anaphylaxis and MACE events – gout flares are not adjudicated).

Summaries of IRs and anaphylaxis will group events by 3 categories:

- Anaphylaxis
- Infusion reactions including anaphylaxis
- Infusion reactions excluding anaphylaxis

Both the investigator-reported and adjudicated events and the associated signs and symptoms will be summarized separately by severity, and the time relative to the most recent pegloticase infusion for each category above. Signs and symptoms will also be summarized by SOC and PT.

Time relative to the most recent pegloticase infusion will be categorized as: during infusion,  $\leq 2$  hours after infusion,  $> 2$  hours to 24 hours after infusion, and  $> 24$  hours after infusion. If the time of the infusion reaction or anaphylaxis is missing, the category will be assigned as “Missing”.

Serious events and the associated symptoms will be summarized by SOC and PT for each category.

The number of events per subject per treatment infusion duration group, the number of events and serious events per infusion, and the number of subjects with the first event by infusion number will be summarized as well for each category. IRs (including anaphylaxis) that occur on the same date will be considered one event.

In addition, the number and percentage of subjects with adjudicated IRs, including anaphylaxis, will be summarized by severity of event using the following categories for both anti-PEG and anti-uricase antibodies:

- ADA status at baseline (positive or negative)
- ADA status post-baseline (positive or negative)
  - ADA positive post-baseline: negative at baseline and positive at any post-baseline time point, or positive at baseline and with an increase in titer at post-baseline timepoint
  - ADA negative post-baseline: defined as negative at all time points, or positive at baseline and without post-baseline increases in titer from baseline titer

MACEs are defined as: including non-fatal myocardial infarction, non-fatal stroke, cardiovascular death, and congestive heart failure. The following search algorithm will be used to identify possible MACEs:

- For cardiovascular death: any fatal cases with following terms

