  - Standardized MedDRA Queries (SMQ): Myocardial infarction (broad), Ischaemic Central Nervous System (CNS) Vascular conditions (narrow); Haemorrhagic central nervous system vascular conditions (narrow), Central nervous system vascular disorders, not specified as haemorrhagic or ischaemic (narrow), Embolic and thrombotic events (arterial, venous, vessel type unspecified and mixed arterial and venous) (narrow), Cardiac failure (broad), shock-associated conditions (narrow), Torsade de pointes/QT prolongation (narrow), Arrhythmia related investigations, signs and symptoms (broad), Cardiomyopathy (broad), Supraventricular tachyarrhythmias (narrow), Ventricular tachyarrhythmias (narrow), Conduction defects (narrow)
  - All PTs under SOC of Cardiac disorders
  - HLT Aneurysm
- For non-fatal myocardial infarction: SMQ Myocardial infarction (broad)
- For non-fatal stroke: SMQ: Ischaemic Central Nervous System (CNS) Vascular conditions (narrow); Haemorrhagic central nervous system vascular conditions (narrow); Central nervous system vascular disorders, not specified as haemorrhagic or ischaemic (narrow)
- Congestive heart failure: SMQ Cardiac failure (broad)

The cardiovascular events identified using the aforementioned criteria and the adjudicated cardiovascular events will be summarized by SOC and PT for the MTX Run-in Period and Pegloticase + MTX Period for the safety analysis set. EAIR of pegloticase and MTX will be summarized for the Pegloticase + MTX Period.

The number and percentage of subjects who experienced a gout flare (recorded in the AE eCRF), and number of gout flares per subject will be summarized for the MTX Run-in Period using the ITT analysis set. Percentages will be based on the number of subjects in the ITT analysis set.

The number and percentage of subjects who experienced a gout flare and number of gout flares per subject during the MTX Run-in Period and the Pegloticase + MTX Period (recorded in the AE eCRF) will be provided for the safety analysis set.

Data for the MTX Run-in Period and Pegloticase + MTX Period will be summarized separately, where applicable.

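### The SAP's search for possible MACEs has no entry for deaths of unknown cause or unwitnessed deaths, which the protocol counts as cardiovascular, so the search-based MACE summary can undercount

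*SAP*

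**What the plan says.** Protocol 9.6.1.2.1.5, under Cardiovascular Events, sets out what sites must record: "The following cardiovascular events will be collected. Major Adverse Cardiovascular Events (MACE) defined as" four components. The cardiovascular-death component names specific causes and closes with "any fatal thromboembolic event, sudden cardiac death, any death of unknown cause and unwitnessed death". The last two of those items need no cardiovascular diagnosis.

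SAP 3.6.3.4 keeps the same components ("MACEs are defined as: including non-fatal myocardial infarction, non-fatal stroke, cardiovascular death, and congestive heart failure") but does not restate what cardiovascular death covers. It goes straight to a coded search: "The following search algorithm will be used to identify possible MACEs". For cardiovascular death the rule is "For cardiovascular death: any fatal cases with following terms". The list holds named standardised MedDRA queries, then "All PTs under SOC of Cardiac disorders", then a high-level term for aneurysm. Nothing follows aneurysm for this component.

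The same section plans two outputs by organ class and preferred term: the events that the search finds, and the adjudicated cardiovascular events. It adds exposure-adjusted rates for the Pegloticase + MTX Period.

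**The concern.** A search for possible events should be at least as wide as the definition it serves, because later steps can remove a case but cannot restore one that was never flagged. The SAP seems to intend a sensitive search, since it uses the broad form of the queries for myocardial infarction, cardiac failure and cardiomyopathy. Yet a fatal outcome alone does not qualify. The case must also carry a listed term, and a death reported with no known cause may have none.

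The protocol assigns exactly these ambiguous deaths to the cardiovascular category. Cardiovascular events are an adverse event of special interest, their incidence is a stated safety endpoint (protocol 9.7.1.5, SAP 1.5.4), and protocol 7.1.3 lists exacerbation of congestive heart failure among the risks of pegloticase. For the search-based summary the omission works in one direction only: it can lower the count and cannot raise it.

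**Working it through.** The plan gives no figure to reproduce here, so the check sets the protocol definition against the search list item by item.

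| Protocol item for cardiovascular death | Entry in the SAP 3.6.3.4 search |
|---|---|
| Myocardial infarction | Myocardial infarction query |
| Stroke | Three central nervous system vascular queries |
| Heart failure | Cardiac failure query |
| Arrhythmic death, sudden cardiac death | Arrhythmia queries and the cardiac organ class |
| Aortic dissection or rupture | Aneurysm high-level term (nearest entry) |
| Fatal thromboembolic event | Embolic and thrombotic queries |
| Death of unknown cause | None |
| Unwitnessed death | None |

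Every other item has an entry or a nearest entry. The last two have none, and no general rule takes in fatal cases without an established cause.

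**Is this an authorised change?** SAP 3.1 lets the SAP override the statistical sections of the protocol. The MACE definition is in protocol 9.6, among the safety variables, not in the statistical methods of 9.7. The readable SAP text gives no reason for a narrower scope. SAP section 4 is partly redacted, so nothing can be drawn from it either way.

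**Size for one such death.** The denominators are the selected cohort of about 110 and the study total of about 130 (110 + 10 + 10; protocol 9.7.9, SAP 1.1.3).

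- Selected cohort: 1/110 = 0.0091, or 0.91 percentage points.
- All cohorts: 1/130 = 0.0077, or 0.77 percentage points.

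**Exposure-adjusted rate.** Assume all 110 subjects are exposed to pegloticase from Day 1 to the Week 22 target day, which is Day 155 in SAP Table 1. Exposure is then 110 × 155 / 365.25 = 46.7 person-years, and one event is 1/46.7 = 0.021, or about 2.1 per 100 person-years. Early discontinuation would shorten the exposure and raise this figure.

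The documents give no expected number of deaths or of MACEs, so these are shifts per death and not forecasts.

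**The case against.** The strongest reply is that the search is not the only route to a MACE. The protocol has these events collected under its wider definition and puts adverse events of special interest on their own eCRF (9.6.1.2.1.5). Cardiovascular events go to the external committee, and SAP 1.3 ties that adjudication to the same protocol section. SAP 3.6.3.4 summarises adjudicated events separately. An unexplained death that is recorded as a cardiovascular event of special interest and adjudicated under the protocol definition would be counted there, whatever the search finds. This stands. It does not remove the mismatch, because the two summaries would still rest on different definitions with no stated reason.

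Nor is a death lost from reporting. Protocol 9.6.1.2.5.1 requires every death to be reported within 24 hours, SAP 3.6.3.2 tabulates events leading to death both on treatment and in follow-up, and SAP 3.6.3.3 lists the adverse events of subjects who died. This also stands.

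The member terms of the listed queries are not in the documents. An unwitnessed death might be coded to one of them and be caught, so the omission concerns deaths that carry no listed term.

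A reader might infer that such a death could never be identified as a MACE, or that the trial's MACE count as a whole is biased downward. Either conclusion needs the search to decide which cases reach the committee. Neither document says so. The committee's responsibilities are left to a charter that is not provided.

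**Conclusion.** The mismatch is real. Followed as written, the search yields a set of possible MACEs narrower than the protocol's own definition, and the search-based summary and its exposure-adjusted rate can undercount accordingly. The adjudicated summary is not shown to be affected.

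The size is hypothetical: 0.9 percentage points per missed death among 110 subjects, or 0.8 among 130. It assumes that at least one subject dies of unknown cause or unwitnessed within a period that the MACE summary covers, and that the death carries no listed term. If MACEs are few, one such death could be the difference between none and one; that too is an assumption. The summary is descriptive, SAP 3.1.1 plans no inferential testing, and MACE is neither the primary nor a secondary endpoint. The case for changing the text rests on a plain inconsistency with a defined event of special interest and on the low cost of removing it.

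A reader might also infer that every death must be sent to adjudication. That belongs to the committee's charter and is not needed to settle this point.

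**What to change.** In SAP 3.6.3.4, add one line to the cardiovascular-death search so that it also takes in fatal cases of unknown cause and unwitnessed deaths. A slightly wider wording would take in all fatal cases without an established non-cardiovascular cause. Either makes the search at least as wide as the protocol definition. If the narrower scope is deliberate, the SAP should say so, give the reason, and footnote the search-based table as using a different definition from the adjudicated one.

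The cost is one line of text and a review of the few fatal cases. SAP 3.1 requires changes before database lock to be made in a SAP amendment. No data collection, visit or clinical rule changes.

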## 9.7.5 Endpoint Analysis

All efficacy analyses will be performed using the mITT set. Baseline characteristics and safety relating to only the MTX Run-in period will be summarized for the ITT set and/or mITT set. All safety analyses relating to pegloticase + MTX period will be summarized using the safety set.

Data will be summarized descriptively by assigned infusion duration regimen, unless otherwise specified. There will be no statistical testing. Continuous variables will be summarized using descriptive statistics (number of subjects, mean, median, standard deviation, minimum and maximum). Categorical variables will be summarized using frequencies and percentages. Unless otherwise specified, baseline is defined as the last non-missing observation prior to the first dose of MTX.

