### 9.7.7 Safety Analysis

Treatment-emergent AEs (TEAEs) during the Run-In period are defined as events with an onset date on or after the first dose of MTX through the first pegloticase infusion, or 30 days after the last dose of MTX for subjects who do not receive pegloticase. TEAEs during the Pegloticase + MTX Period are defined as events that occur after the start of the first pegloticase infusion through 30 days after the last dose of pegloticase and/or MTX (whichever is later).

TEAEs during the MTX Run-in Period will be summarized with the ITT population and TEAEs during the Pegloticase + MTX Period will be summarized with both the ITT and mITT populations. TEAEs during any period (MTX Run-in Period or Pegloticase + MTX Period) will be summarized for the mITT population. AEs that occur more than 30 days after the last dose of pegloticase and/or MTX through the 3-month Follow-up visit will also be summarized. The number and percentage of subjects experiencing AEs will be summarized by system organ class and preferred term. Summaries by maximum severity and relationship to MTX and pegloticase will also be provided. SAEs and AEs leading to discontinuation of MTX and pegloticase will be presented by system organ class and preferred term.

Incidence of IRs, gout flares and other AEs of special interest will be summarized.

The following safety endpoints will be summarized descriptively along with a two-sided 95% exact (Clopper-Pearson) confidence interval:

- The proportion of subjects who experienced IR leading to slowing down of the infusion rate or discontinuation of treatment.
- The proportion of subjects who were able to complete all infusions over the assigned treatment duration length or a lesser time, without clinically requiring an increased infusion time.
- The proportion of infusions completed over the assigned duration length or a lesser time, without clinically requiring an increased infusion time.

The time to subjects experiencing first IR leading to slowing down of the infusion rate or discontinuation of treatment, and time to subjects first IR will both be analyzed using Kaplan Meier (KM) estimates of the time to event will be reported along with the corresponding quartiles and a 95% CI for the median time if there are sufficient number of events to perform the analysis.

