## 2 Analysis Sets

The statistical analyses will be performed based on the following analysis sets:

- Intent-to-treat (ITT) analysis set: all subjects who take at least one dose of MTX.
- Modified intention-to-treat (mITT) analysis set: all subjects who receive at least 1 dose of pegloticase. All efficacy analyses will be conducted on the mITT analysis set.
- Safety analysis set: all subjects who receive at least 1 dose of pegloticase. All safety analyses will be conducted on the safety analysis set.
- Pharmacokinetic (PK) set: all subjects who receive at least 1 dose of pegloticase and have a post-pegloticase sample evaluable for PK analysis.

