### 3.6 Safety Analysis

#### 3.6.1 General Conventions

Unless otherwise specified, safety analyses will be based on the safety analysis set and the ITT analysis set, depending on the treatment period. The ITT analysis set will be used for analysis of safety data during the MTX Run-in Period prior to Day 1 and the safety analysis set will be used for analysis in the Pegloticase + MTX Period or summaries across both treatment periods. Summaries will be presented by “as-assigned” infusion duration group. Analyses done by “as-treated” group may be done, if warranted.

Refer to Section 3.1.6 for additional details regarding infusion duration group for reporting.

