### 3.6.3 Adverse Events

#### 3.6.3.1 Definitions by Period

AEs will be classified as pre-treatment, treatment-emergent AEs (TEAEs) during the MTX Run-In Period, TEAEs during the Pegloticase + MTX period, or Follow-up AEs. The AE's will be classified as follows:

- Pre-treatment: Onset date prior to the first dose of MTX.
- TEAE during the MTX Run-in Period: Onset date on or after the first dose of MTX until the first pegloticase infusion.
- For subjects who do not receive pegloticase, also include AEs with onset date within 30 days after the last dose of MTX.
- TEAE during the Pegloticase + MTX Period: Onset date on or after the start of the first pegloticase infusion through 30 days after the last dose of pegloticase and/or MTX (whichever is later).
- Follow-up AE: Onset date >30 days after last dose of pegloticase and/or MTX (whichever is later).

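### Run-in MACE is summarized only in subjects later dosed with pegloticase, so run-in events in MTX-exposed subjects who never reach Day 1 enter no MACE incidence

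*SAP*

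**What the plan says.** SAP 3.6.3.4 defines MACE by a MedDRA search, has cardiovascular events adjudicated, and says that both the search-identified and the adjudicated events are "summarized by SOC and PT for the MTX Run-in Period and Pegloticase + MTX Period for the safety analysis set". The section's opening sentence names the same set: "Major Adverse Cardiovascular Events (MACE) will be summarized for the safety analysis set by infusion duration group". SAP section 2 gives the definition: "Safety analysis set: all subjects who receive at least 1 dose of pegloticase". ITT, by contrast, needs only one dose of MTX.

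The general rule for this period, in SAP 3.6.1, is different: "The ITT analysis set will be used for analysis of safety data during the MTX Run-in Period prior to Day 1". That rule is a default and yields where a section specifies otherwise. Later in SAP 3.6.3.4, the other AESI with run-in data follows the default: the number of subjects with a flare and the "number of gout flares per subject will be summarized for the MTX Run-in Period using the ITT analysis set", with a safety-set version added.

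The protocol speaks to this twice. Section 9.7.5 says "safety relating to only the MTX Run-in period will be summarized for the ITT set and/or mITT set"; section 9.7.7 says "TEAEs during the MTX Run-in Period will be summarized with the ITT population".

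**The concern.** The run-in MACE table is restricted to people who later received pegloticase, so it conditions on something that happens after the events it counts. Three kinds of event drop out:

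- a cardiovascular death before Day 1;
- a non-fatal run-in event after which the subject is not dosed;
- an event after MTX was stopped in a subject who never reached Day 1.

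The SAP's own definition of a run-in TEAE includes the third kind: "For subjects who do not receive pegloticase, also include AEs with onset date within 30 days after the last dose of MTX". On the safety set that clause can never operate.

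The second kind has a plausible route. Eligibility is rechecked on Day 1 (Protocol 2.1), non-compensated heart failure is an exclusion (Protocol 9.4.2), and new or increasing dyspnea reflecting MTX intolerance makes a subject a run-in screen failure (Protocol 9.5.7.3.2.2). Congestive heart failure is one of the SAP's MACE components.

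At stake is whether a reader of the run-in MACE table sees all serious cardiovascular events among MTX-exposed subjects. As written, the table could show no adjudicated run-in MACE when one had occurred.

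**Working it through.** **1. Which set is named for run-in summaries**

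| Run-in output | SAP section | ITT | Safety set |
|---|---|---|---|
| Overall TEAE summary | 3.6.3.2 | yes, but no AESI line | – |
| SOC/PT tables with a run-in entry (8 rows) | 3.6.3.3 | all 8 | all 8 |
| Gout flares | 3.6.3.4 | yes | yes |
| MACE, search-identified and adjudicated | 3.6.3.4 | **no** | yes |
| MACE listing, reported and adjudicated | 3.6.3.3 | listing only, no incidence | – |

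MACE is the only run-in incidence summary in this table without an ITT version. The overall summary for the Pegloticase + MTX Period has an AESI line; the ITT run-in overall summary does not.

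**2. Who is left out.** Subjects with at least one MTX dose and no pegloticase. The plan expects them: the run-in disposition table in SAP 3.3.1 counts MTX screen failures. Neither document gives their number. Run-in events in subjects who are later dosed remain counted, including events that later prove fatal.

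**3. Illustrative size.** Inputs:

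- Dosed subjects: 130, the planned minimum in Protocol 9.7.9.
- ITT size *N*: not given; assumed 140 to 180, that is, 10 to 50 never dosed.
- Intervals: Clopper-Pearson, two-sided 95%.

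| Scenario | Safety set | ITT, *N* = 140 | ITT, *N* = 180 |
|---|---|---|---|
| One event, never-dosed subject | 0/130 = 0% (0 to 2.80) | 1/140 = 0.71% (0.02 to 3.92) | 1/180 = 0.56% (0.01 to 3.06) |
| Two events, one in a never-dosed subject | 1/130 = 0.77% (0.02 to 4.21) | 2/140 = 1.43% (0.17 to 5.07) | 2/180 = 1.11% (0.13 to 3.96) |
| One event, dosed subject | 1/130 = 0.77% (0.02 to 4.21) | 1/140 = 0.71% (0.02 to 3.92) | 1/180 = 0.56% (0.01 to 3.06) |

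**4. Direction of the difference.** Let *d* be the number of subjects with a run-in MACE who were dosed and *n* the number who were never dosed. The safety-set figure is lower than the ITT figure when

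*d*/130 < (*d* + *n*)/*N*, which rearranges to *n*/(*d* + *n*) > 1 − 130/*N*.

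- *N* = 140: 10/140 = 7.1%
- *N* = 150: 20/150 = 13.3%
- *N* = 180: 50/180 = 27.8%

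So the safety-set rate is too low only if never-dosed subjects account for a larger share of run-in MACE than of the ITT set. The documents do not give that share. In the third scenario the safety-set figure is slightly the higher one.

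**The case against.** The choice may be deliberate. SAP 3.6.1 also assigns the safety set to summaries that span both treatment periods, and the MACE sentence names both periods together. SAP section 2 says that safety analyses in general use the safety set. Protocol 9.7.5 allows run-in safety on ITT, mITT or both, and the mITT set has the same definition as the safety set, so there is no breach. The protocol's safety endpoint refers to events attributable to the drug combination, which a never-dosed subject has not received. The omitted events are not lost: they appear in the ITT run-in tables of TEAEs, SAEs and deaths and in the MACE listing with period of onset, which is where the 30-day clause does its work. The run-in lasts 4 weeks, Protocol 9.4.2 excludes recent acute coronary syndrome and uncontrolled arrhythmia, and few events are likely.

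Most of this stands, and it limits the point to an inconsistency within the SAP. It does not supply the missing figure. No ITT output groups events as MACE or carries the adjudication result, so the adjudicated count among all MTX-exposed subjects would have to be assembled from the listing. The SAP gives no reason for treating MACE differently from gout flares.

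A further doubt also stands. Footnote 25 of the Schedule of Assessments provides an AE and SAE contact 30 days after the last MTX dose. Protocol 9.4.4.3, written for screen failures, mentions only pregnancy-related contacts. The documents also do not say whether events in never-dosed subjects go to adjudication. Capture of events after MTX is stopped may therefore be incomplete.

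**Conclusion.** The concern holds, as a minor point worth considering. Run-in MACE incidence is planned only for subjects who survive and qualify for Day 1, and this departs from how the SAP handles its other run-in adverse event summaries. It is not a protocol breach, and no primary or secondary endpoint or infusion-duration decision is affected.

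The true size cannot be calculated, because the documents give neither the number of never-dosed subjects nor a MACE rate. Under the assumed ITT sizes the differences are fractions of a percentage point, they can go either way, and the confidence intervals overlap almost fully. What is lost is sight of individual serious events, not accuracy in an estimated rate.

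**What to change.** In SAP 3.6.3.4, add a run-in summary of cardiovascular events on the ITT set, both search-identified and adjudicated. Use the run-in TEAE definition in SAP 3.6.3.1, including the 30 days after the last MTX dose for never-dosed subjects, with the ITT count as denominator. Keep the safety-set version beside it, as is done for gout flares. State that events in never-dosed subjects are sent for adjudication, and confirm that the 30-day contact in footnote 25 applies to run-in screen failures.

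The cost is about one table column: SAP 3.1.2 already presents ITT run-in results as a single MTX group. AEs and SAEs are collected from consent, so no new study procedure is needed provided the footnote 25 contact is made. SAP 3.1.1 allows supportive analyses to be added without an amendment.
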